- If the participant experiences hypoglycemia (PG $< 3.9 \text{ mmol/l}$) during the exercise session, exercise will be stopped, and 15 g of oral glucose will be provided. The participant will then rest for the remaining time of the exercise period, and afterwards move on to the post-exercise observation period. If the PG has not risen to $> 3.9 \text{ mmol/l}$ after 15 min, another 15 g of oral glucose will be provided. In the unlikely event that the oral glucose consumption should not prove sufficient to

establish euglycemia, an intravenous glucose infusion will be provided. In both cases, the nadir PG level will be carried forward to the end of the observation period.

Post-exercise observation:

- After ending the exercise session, PG will be monitored for another 60 mins before concluding the study visit.
- The participants will consume a standardized low-glycemic index, carbohydrate-based meal (0.75 g carbohydrates per kg body weight) with their usual meal-time insulin dose.
- Following consumption of this meal, participants will be discharged from the laboratory.

The study visit will be stopped in the following circumstances:

- Inability to perform the exercise session.
- Cardiac discomfort.
- Onset of angina or angina-like symptoms.
- Shortness of breath, wheezing, leg cramps, or claudication.
- Signs of poor perfusion: light-headedness, confusion, ataxia, pallor, cyanosis, nausea, or cold and clammy skin.
- Failure of the testing equipment.

Please see figure 2 illustrating the details for visit B

Trial day schematic – 2.5 hr. Laboratory phase				
Phase	Pre-exercise (rest)	Exercise	Post-exercise (rest)	
	 Lab arrival T= -45 min T= -30 min T= -15 min T= 0 min	 MICE " 60 % VO2max 45 mins	T= +45 min T= +60 min T= +75 min T= +105 min	 Lab departure
Blood sampling*	T= -45, -30, -15, 0 min	Every 5 min	T= +45, +60, +75, +105 min	
Glucagon (s.c. 150 µg)	-	T=0	-	
SG target to 8.3	T=-15	-	T=+60**	

Figure 1: Visit B, *PG, lactate and ketone bodies, metabolomics and hormones; ** the sensor glucose (SG) target will return to the initial value. MICE: Moderate intensity continuous exercise. Subcutaneous glucagon injection pertains to visit B only.

10. Study devices

The AHCL system used in this study is the Minimed 780G pump with the Guardian 3 or Guardian 4 sensor and receiver.

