12.1 Primary endpoint

- Difference in percentage of time in target glucose range (PG: 3.9 - 10.0 mmol/l) during and for 1-hour after dynamic physical exercise (_{0 min to +105 min}) between visits B and C.

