12.2 Secondary endpoints

- Difference in incidence rate of hypoglycemic events ($PG < 3.9 \text{ mmol/l}$) $(0 \text{ min to } +105\text{min})$ between visits B and C
- Difference in time (min) to hypoglycemia ($PG < 3.9 \text{ mmol/l}$) $(0 \text{ min to } +105\text{min})$ between visits B and C
- Difference in percentage of time below target glucose range ($PG < 3.9 \text{ mmol/l}$) $(0 \text{ min to } +105\text{min})$ between visits B and C
- Difference in percentage of time above target glucose range ($PG > 10.0 \text{ mmol/l}$) $(0 \text{ min to } +105\text{min})$ between visits B and C
- Difference in incidence rate of hyperglycemia ($PG > 10.0 \text{ mmol/l}$) $(0 \text{ min to } +105\text{min})$ between visits B and C
- Difference in nadir PG concentration $(0 \text{ min to } +105\text{min})$ between visits B and C
- Difference in peak PG concentration $(0 \text{ min to } +105\text{min})$ between visits B and C
- Difference in incremental peak PG concentration $(0 \text{ min to } +105\text{min})$ between visits B and C
- Difference in mean PG concentration $(0 \text{ min to } +105\text{min})$ between visits B and C
- Difference in PG Area Under the Curve (AUC) $(0 \text{ min to } +105\text{min})$ between visits B and C
- Difference in standard deviation in PG concentrations $(0 \text{ min to } +105\text{min})$ between visits B and C
- Difference in coefficient of variation in PG concentrations $(0 \text{ min to } +105\text{min})$ between visits B and C

13. Statistical considerations

To our knowledge, this is the first study to evaluate the glucose effects of s.c. injection of glucagon around exercise in individuals with AHCL-treated T1D. This is a proof of concept study to assess the use of low-dose glucagon in persons type 1 diabetes performing exercise during treatment with a hybrid closed-loop system with a control arm as a comparator on a sub-group of the full participant cohort. As such, no power calculation has been performed. The sample size of 16 participants has been chosen from a feasibility perspective. It is anticipated that at least 10 of whom will proceed to complete the control arm for comparative purposes in this proof-of concept study.

14. Safety and risk assessment

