If PG drops below 3.9 mmol/l or the participant experiences unbearable symptoms of hypoglycaemia, 15 g of oral glucose will be administered, and subsequent close monitoring of PG will be ensured. The investigator can, at any given time, choose to discontinue the study visit if deemed necessary for safety reasons. Likewise, individuals can withdraw from the study at any given time.

In general, exercise is associated with a risk of hypoglycemia for people with T1D. In this study, some participants might experience an episode of mild hypoglycemia (PG level between 3.0 to 3.9 mmol/l). Symptoms of mild hypoglycemia (e.g. shakiness, dizziness, sweating, palpitations, hunger or headache) are relatively modest and previously experienced by all people with T1D. The risk of severe hypoglycemia during the study is very low, as the participants will be closely monitored with frequent glucose measurements and continuous clinical evaluation. Moreover, an IV catheter is maintained throughout the study visit which will enable fast elevation of PG if needed.

Administration of glucagon carries a small risk of transitory side effects with symptoms such as nausea and headache being the most frequent. However, as dose sizes in this study are small, the frequency of these side effects is expected to be low and the intensity mild.

The amount of blood extracted during the study visit equals about 250 ml (a regular blood donation amounts to approximately 500 ml), which is not expected to cause any adverse effects.

Performing venipuncture may inflict a short pain and a risk of a small hematoma, and there is a minimal risk of infection at the puncture site.

With regards to all other planned study procedures, the risk of complications or adverse events is negligible and certainly outweighed by the benefits of this study.

A study investigator, who also is a medical doctor, will always be present at the research facility during conduct of the study.

15. Adverse event management

Definition of adverse event (AE):

Any untoward medical occurrence in a patient or clinical investigation subject administering/using a product (which does not necessarily have to have a causal relationship with this treatment). An adverse event can therefore be any unfavorable and unintended sign (including an abnormal laboratory finding), symptom, or disease temporally associated with the use of a product, whether considered related to the product.

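### The nadir carry-forward after rescue glucose is tied to rescues that start during exercise, but the endpoints run 60 minutes longer, so the same low glucose scores differently before and after +45 min

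*Combined protocol and SAP*

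**What the plan says.** Three parts of the protocol bear on this.

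- **Section 9, Intervention and exercise.** The bullet concerns PG below 3.9 mmol/l "during the exercise session, exercise will be stopped, and 15 g of oral glucose will be provided". A second dose follows if PG has not recovered "after 15 min, another 15 g of oral glucose will be provided", and intravenous glucose is the fallback. The bullet ends: "In both cases, the nadir PG level will be carried forward to the end of the observation period". The two cases are the oral and the intravenous rescue described in that same bullet.
- **Section 9, Post-exercise observation.** "After ending the exercise session, PG will be monitored for another 60 mins before concluding the study visit". No rescue or scoring rule is given for this hour.
- **Section 14, Safety and risk assessment.** The rescue instruction here reads: "If PG drops below 3.9 mmol/l or the participant experiences unbearable symptoms of hypoglycaemia, 15 g of oral glucose will be administered". No period is stated, symptoms are a second trigger, and scoring is not mentioned.

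The primary endpoint in Section 12.1 is "Difference in percentage of time in target glucose range" (PG 3.9 to 10.0 mmol/l) over 0 to +105 min, compared between visits B and C. The secondary endpoints in Section 12.2 use the same window and include "Difference in time (min) to hypoglycemia". Sections 12 and 13 do not say how PG after a rescue is handled. On numbers, Section 13 plans 16 participants and adds: "It is anticipated that at least 10 of whom will proceed to complete the control arm".

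**The concern.** The carry-forward exists to keep rescue glucose out of the outcome. Without it, a visit that needed treatment would look recovered because of the treatment. As worded, that protection applies only to rescues that start in the first 45 of the 105 min. The other 60 min, 57.1% of the window, has no rule.

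The plan therefore leaves two scoring methods within one endpoint, and the time of the low decides which applies. Time to hypoglycaemia is a secondary endpoint, so the plan foresees that glucagon may delay a low rather than prevent it. A low that moves from late exercise at one visit to the post-exercise hour at the other would change scoring method between the two halves of a pair.

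Time below range is affected in the mirror image. Mean PG, AUC, SD, CV and possibly peak PG are affected too. Nadir PG and time to the first PG below 3.9 mmol/l are much less exposed.

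**Working it through.** The plan gives no figure to reproduce: Section 13 states that there is no power calculation, and no variance or rescue frequency appears.

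**Inputs from the documents.** Window 105 min; exercise 0 to +45 min; post-exercise hour +45 to +105 min; at least 10 pairs expected, 16 at most.

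**Assumptions.** PG is in range until the rescue and never exceeds 10.0 mmol/l. PG returns to 3.9 mmol/l or above after r = 15 or 30 min. The lower value is the plan's own re-check time after oral glucose; the upper is assumed.

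**Formulas**, for a rescue at t min:
- carry-forward: time in range = t / 105
- as measured: time in range = (105 − r) / 105, where r is cut off at 105 − t
- gap = the difference; effect of one unbalanced rescue on the mean of n pairs = gap / n

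| Rescue at | Carry-forward | As measured, r = 15 / 30 | Gap, points | Mean of 10 pairs |
|---|---|---|---|---|
| +50 | 50/105 = 47.6% | 85.7% / 71.4% | 38.1 / 23.8 | 3.8 / 2.4 |
| +60 | 60/105 = 57.1% | 85.7% / 71.4% | 28.6 / 14.3 | 2.9 / 1.4 |
| +75 | 75/105 = 71.4% | 85.7% / 71.4% | 14.3 / 0 | 1.4 / 0 |
| +90 | 90/105 = 85.7% | 85.7% / 85.7% | 0 / 0 | 0 / 0 |

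I take +60 as the reference case because it is a sampling time in both the Section 9 text and the visit schematic. The +50 row relies on the text's 5-min sampling up to +60; the schematic, as it reads, goes from +45 straight to +60. With all 16 pairs, the +60 effect is 28.6/16 = 1.8 to 14.3/16 = 0.9 points. Three such participants among 10 pairs would give 3 × 1.43 = 4.3 to 3 × 2.86 = 8.6 points.

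**Direction.** Two illustrations with r = 15:
- *Delay.* Visit C is rescued at +40 and visit B at +60. On the literal text, C is carried forward (40/105 = 38.1%) and B is as measured (85.7%), a difference of 47.6 points. Carry-forward at both visits gives 57.1 − 38.1 = 19.0. As measured at both gives 85.7 − 85.7 = 0. The literal text inflates the benefit against either consistent rule.
- *Prevention.* Visit B has no low (100%) and visit C is rescued at +60. As measured, the benefit is 15/105 = 14.3 points; under carry-forward it is 45/105 = 42.9. Here the literal text shrinks the benefit relative to carry-forward.

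**Symptom rescues at PG of 3.9 or above.** The nadir is itself in range, so carrying it forward or using measured PG gives the same time in range while PG stays at or below 10.0. Mean PG can differ. Assume a rescue at +30 and a rise of R mmol/l over 30 min, then flat. The difference is (0.5 × 30 × R + 45 × R)/105 = 0.57R, so 0.57 to 1.71 mmol/l for R = 1 to 3, or 0.06 to 0.17 on the mean of 10 pairs.

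**The case against.** The strongest reply is about intent. The rule already holds the carried value through the post-exercise hour, so a team could naturally apply it to a rescue that starts in that hour. If so, the effect is zero. That is plausible, but the text does not say it, and in an unblinded study the choice should not wait until the data are seen.

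The second reply is that every figure is conditional. It stands: rescue times and recoveries are assumed, and the documents give no frequency, which may be zero. The delay example is also chosen to straddle +45 min, and it vanishes if both visits are scored as measured. It shows that the scoring is inconsistent, not what size of effect to expect.

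Third, this is an unpowered proof-of-concept study without randomisation. That lowers the stakes, but a primary endpoint value should still be defined for each visit.

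Stronger readings are tempting, and the documents do not support them. A reader might infer that the gap favours glucagon; the two illustrations run in opposite directions. A reader might infer that symptom rescues distort the primary endpoint; they leave time in range unchanged while PG stays at or below 10.0 mmol/l. Some such visits may also end under the Section 9 stopping list. And a reader might infer that reasons for rescue will go unrecorded; the case report form is not among the documents, and glucose values are kept in the analyser's source files.

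**Conclusion.** The point holds in limited form. As written, the carry-forward is triggered only by PG below 3.9 mmol/l during exercise, while rescue glucose and all the endpoints extend beyond it. Taken literally, the primary endpoint is scored by two methods according to when the low occurs.

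The size is 14 to 29 points on one visit's time in range for a rescue at +60 min, or 1.4 to 2.9 points on the mean of 10 pairs for each unbalanced rescue. It is larger for earlier post-exercise rescues and fades to nothing by +90 min. This rests on recovery in 15 to 30 min, PG in range before the rescue, and no excursion above 10.0 mmol/l. Net direction and frequency cannot be determined from the documents, and the effect is zero if carry-forward is already applied after exercise. The wording should be corrected because the correction is nearly free, not because a large bias has been shown.

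**What to change.** - In Sections 9 and 12, state that after any rescue for PG below 3.9 mmol/l between 0 and +105 min, at either visit, the nadir PG is carried forward to +105 min.
- Prespecify one sensitivity analysis that uses PG as measured at both visits.
- For symptom rescues at PG of 3.9 mmol/l or above, record the PG and the reason, and report the count by visit. Adverse event reporting will not supply this: Section 15 excludes hypoglycaemia and hyperglycaemia handled by the safety procedures and describes collection for visit B only. No carry-forward, stop-exercise rule or extra sampling is needed for these rescues.

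The cost is a few sentences, a record of PG and reason at each symptom rescue, and one extra analysis. The downside is that carry-forward replaces some measured post-rescue values with a flat one, which affects mean PG, AUC, SD and CV. The plan already accepts this for exercise-phase rescues, and the sensitivity analysis shows how much it matters.

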In recent years, a number of studies have successfully demonstrated that subcutaneous (s.c.) low-dose glucagon can be utilized to effectively treat insulin-induced and exercise-induced mild hypoglycemia in people with T1D (13–15). Likewise, s.c. infusion of low-dose glucagon in dual-hormone AHCL systems has shown promising results in people with T1D (9).

This will be the first feasibility/pilot study to evaluate the use of glucagon provision for **hypoglycemia prevention** during exercise in people with type 1 diabetes using AHCL therapy; the **“HYPO-AVOID”** study. The results of this research may contribute useful data that helps identify glycaemic management strategies that encourage patient safety, and greater exercise participation in people with T1D.

2. Hypothesis

We hypothesize that low-dose glucagon administered s.c. before aerobic exercise is superior to no glucagon regarding glucose control around exercise in people with T1D using AHCL therapy.

3. Study objective

To compare the effect of low-dose glucagon (single 150 µg dose) administered immediately before aerobic exercise versus a control trial without glucagon on glucose responses during and after exercise in individuals with AHCL-treated T1D.

4. Study design

The HYPO-AVOID study consists of a screening visit (visit A) and two additional study visits (visit B and visit C) completed in a sequential order. During study visit B (detailed in section 9), participants will receive s.c. administration of 150 µg glucagon prior to a 45-min moderate intensity continuous exercise session and subsequently continue into a 1-hour post-exercise observation period. During study visit C the exact same procedures will be followed with the omission of glucagon.

5. Subject selection

The HYPO-AVOID study will include individuals with AHCL-treated (Minimed Medtronic 780G) T1D, and the participants will be recruited from the clinic at Steno Diabetes Center Copenhagen.

A written participant information will be handed out along with the brochure: "Forsøgspersoners rettigheder i et sundhedsvidenskabeligt forskningsprojekt".

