Participants must refrain from alcohol consumption and strenuous physical exercise 24 hours before the study visit. Participants will also be instructed not to administrate insulin boluses 4 hours prior to the start of the study visit. Conservative administration of glucose tablets prior to study initiation will be allowed to avoid hypoglycemia.

Individuals will be instructed to avoid hypoglycemia (defined as a sensor value and/or finger prick value $< 3.9 \text{ mmol/l}$) 24 hours before each study visit. Hypoglycemia will be avoided by frequently measuring their plasma glucose (PG) and by setting the CGM low alarm to 4.5 mmol/l. If the participant has a low alarm on the CGM, it should always be ensured by Blood Glucose Monitoring (BGM). CGM data for the previous 24 hours will be evaluated on each study day to check for episodes of hypoglycemia. If hypoglycemia ($< 3.0 \text{ mmol/l}$) has been present, the study visit is postponed for at least one day.

9. Study visit procedures

Arrival and preparation:

In-clinic phase:

- Participants will arrive at the research facility at Steno Diabetes Center Copenhagen in the morning following an overnight fast (incl. coffee, medicine and tobacco). Conservative administration of glucose tablets prior to study initiation will be allowed to avoid hypoglycemia.
- A urine HCG test will be performed for all female subjects with childbearing potential. If the test is positive, the primary investigator will inform the subject of the test result and the visit will be cancelled.
- A peripheral venous catheter will be inserted in the antecubital vein to draw blood.
- 15 mins before exercise, the target glucose level will be increased to 8.3 mmol/L in the AHCL system until 15 mins after end of exercise.
- Venous blood glucose sampling will be taken in 15-min intervals from -45 to -15 mins, 5-min intervals from -15 to +60 mins and 15-min intervals from +60 to +105 mins. Samples will be analyzed immediately to determine blood glucose concentrations and later to characterize the metabolomic, hormonal and physiological responses.

Intervention and exercise:

- Immediately before exercise start ($t = 0$), 150 μg s.c. glucagon will be administrated in the abdominal area at visit B. No glucagon will be given at visit C.
- Subsequently, participants will start exercising on an ergocycle with moderate intensity (60% of $\text{VO}_2\text{-max}$, which is available from the CPET) for 45 mins.

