Reporting of AE, SAE, SAR and SUSAR:

All events meeting the definition of an AE will be collected and reported. The causality is evaluated by the investigator. AEs will be collected from the beginning of the study day (visit B) until 12 hours after initial dosing of glucagon as the effects of glucagon are not expected to extend beyond this time frame. SAEs, SARs will initially be reported to the sponsor within 24 hours after the investigator has become aware of the adverse event. All follow-up data will be described in detail in a SAE-formula and subsequently given to the sponsor within 24 hours of obtaining the new knowledge. Previous non-serious AEs that becomes SAEs will follow the reporting of SAEs. It is the sponsor who will evaluate if the reported SAE and SAR are a SUSAR.

Sponsor will ensure that all information on SUSARs that are fatal or life-threatening is recorded and reported to the Danish Health and Medicines Authority (web-based form) as soon as possible and no later than seven days after the sponsor becomes aware of such possible side effects. Within eight days after reporting, sponsor will provide the Danish Health and Medicines Authority with all relevant information about the sponsor's and investigator's response to the alert and consequences for the further course of the study conduct.

All other SUSARs will be reported to the Danish Health and Medicines Authority within 15 calendar days after sponsor becomes aware of them. Moreover, a safety report will be compiled each year, which will be sent to the Regional Scientific Ethics Committee and Danish Medicines Agency.

Reporting at the end of the study:

All AEs and SAEs will be included and uploaded in the results section of the study EudraCT (<https://eudraact.ema.europa.eu/>). The link to this report will be sent to the Danish Health and Medicines Authority and the Regional Scientific Ethics Committee within 12 months after the last participant has completed the project. SARs are reported to the Danish Health and Medicines Authority and the Regional Ethics Committee annually.

16. Extraction of biological samples

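### The only stated AE collection window names visit B and ends 12 h after glucagon; control visit C has no window, so non-serious AE data may be one-sided

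*Combined protocol and SAP*

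**What the plan says.** Section 15 (Reporting of AE, SAE, SAR and SUSAR) opens with a general commitment: "All events meeting the definition of an AE will be collected and reported". It names no visit. Soon after comes the only collection period in the document: "AEs will be collected from the beginning of the study day (visit B) until 12 hours after initial dosing of glucagon". The rest of that sentence justifies the period by the expected duration of glucagon's effects.

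The AE definition, also in Section 15, refers to a patient or "clinical investigation subject administering/using a product" and to signs, symptoms or disease "temporally associated with the use of a product". It does not say which product is meant.

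Section 4 describes visits B and C as "completed in a sequential order" and adds: "During study visit C the exact same procedures will be followed with the omission of glucagon". Section 9 confirms: "No glucagon will be given at visit C".

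At the end of the study, Section 15 promises: "All AEs and SAEs will be included and uploaded in the results section of the study EudraCT".

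**The concern.** A control visit helps in describing tolerability only if events are sought there in the same way as at the active visit. Section 14 expects nausea and headache as the most frequent effects of glucagon. The protocol also names sources of events that have nothing to do with glucagon: nausea is among the signs for stopping a study visit (Section 9, not limited to visit B), and venipuncture may cause pain or a small hematoma (Section 14). Visit C has the same ride and the same catheter without the injection, so it is the trial's only internal background for such events.

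If non-serious AEs are collected at visit B alone, the AE upload will contain visit B events only. A reader could not tell how often the same symptoms occur without glucagon. Events not recorded at visit C cannot be recovered reliably later.

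**Working it through.** The plan has no figure to reproduce here. The check is a reading of the text plus simple counts.

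**Step 1: does the stated window fit each visit?**

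| | Visit B | Visit C |
|---|---|---|
| Named in the collection sentence (Section 15) | yes | no |
| Glucagon dosing to count 12 h from (Section 9) | yes, at t = 0 | none |
| Exercise, sampling, 60 min observation (Sections 4, 9) | yes | yes |
| Stated hours of AE collection | about 12.75 h | none stated |

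The 12.75 h takes arrival at -45 min (visit schematic, Section 9) as the beginning of the study day: 0.75 h + 12 h = 12.75 h.

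**Step 2: does any other text supply a visit C window?**
- The general commitment in Section 15 covers events that meet the AE definition, so its reach depends on what the product is. If it is glucagon, visit C falls outside. If it includes the pump, sensor or insulin, visit C falls inside. No time limit is given on either reading.
- The Section 4 sentence on identical procedures follows an account of the exercise and observation session. It does not mention AEs. Even if it carried AE collection over to visit C, a period that ends 12 h after a dose that is not given has no end.
- Section 11.1 invites participants to report suspected reactions to the study medication after discharge. This is voluntary and tied to the drug, so it is not a visit C window.
- The sentence on serious events is triggered by the investigator's awareness and names no visit, so serious events at visit C may still be reported.

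None of the four gives visit C an end time.

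**Step 3: how much of the study is affected?** Section 13 gives 16 participants, of whom at least 10 are expected to complete the control arm. Assuming all 16 attend visit B:
- Visit C share of exercise visits, lower: 10 / (16 + 10) = 38.5%.
- Visit C share, upper: 16 / (16 + 16) = 50%.
- Exposed participants who may have no visit C: up to (16 - 10) / 16 = 37.5%.

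These are shares of visits and people, not of events. No background AE rate is given, and none is assumed.

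**Step 4: what could visit C data show?** With 0 events in n visits, the exact two-sided 95% upper limit is 1 - 0.025^(1/n):
- n = 10: 1 - 0.025^(1/10) = 30.8%.
- n = 16: 1 - 0.025^(1/16) = 20.6%.

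Visit C would therefore give a description, not a precise background rate.

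**The case against.** The strongest defence is that the window deliberately follows drug exposure. It ends when glucagon's effects are expected to be over, visit C comes later and involves no glucagon, and the objective and endpoints concern glucose only. That explains the wording. But the window already opens before dosing, so collection is not strictly tied to exposure, and the explanation does not say whether AEs are sought at visit C.

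A second defence is that visit C is covered already. The general commitment names no visit. The AE definition speaks loosely of a product, whereas Section 15 elsewhere refers specifically to the study medication or the trial product, and participants at visit C are using a pump, a sensor and insulin. This stands in part: it makes non-collection at visit C likely rather than established. It does not supply an end time.

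Third, the gain is modest. This stands. Any comparison is unblinded, in fixed order and limited to about 10 to 16 pairs. Because visit C follows visit B, it cannot inform the causality call when a visit B event is assessed.

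Three stronger inferences are tempting but not supported:
- *Visit C events are certainly lost.* The text does not settle this, and the documents do not show whether the eCRF has AE fields for visit C.
- *Headache from hypoglycemia shows the need for visit C data.* Section 15 does not count hypoglycemia handled by the safety procedures as an AE at either visit, so a headache with such an episode might go uncounted even after the fix. Nausea from exercise and venipuncture effects are the sounder examples.
- *The 24 h after discharge in Section 11.1 contradicts the 12 h in Section 15.* The first is voluntary reporting of suspected drug reactions and the second is active collection. The difference shows no lost data.

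**Conclusion.** The point holds as a low-severity gap in wording. The only stated AE window names visit B and ends relative to a dose that visit C does not include. Read literally, 38% to 50% of exercise visits have no stated period of AE collection, and the final description of non-serious AEs would be one-sided. This rests on the collection sentence governing what staff actually do, on all 16 participants attending visit B, and on 10 to 16 attending visit C. A broader reading is possible, but the end time at visit C is undefined on every reading, so the text needs repair either way. The glucose endpoints are untouched, and AEs are not a listed endpoint.

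**What to change.** In Section 15:
1. State that AEs are collected at both visits B and C, by the same method, from the beginning of each study day to the same time after exercise start (t = 0). Because glucagon is given immediately before exercise start, keeping 12 h would leave the visit B window essentially unchanged.
2. Clarify that the product in the AE definition does not exclude visit C, and state that SAE reporting applies at all visits.
3. Report AEs descriptively by visit, with everyone who attended that visit as the denominator. A paired summary of those who completed both visits may be added but should not replace this, since up to 6 of 16 exposed participants may have no visit C.
4. For visits already run, report visit C according to what was actually done. Show it as not collected, rather than as zero, only where AEs were in fact not collected.

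The cost is an amendment to the wording, a few more AE records, and a contact after visit C up to the chosen end time. Section 14 already has a medically qualified investigator present during study conduct. Whether the eCRF needs new fields cannot be seen from the documents.
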